Appendix 6 Euro-QoL5D-5L

A sample form for the EQ-5D-5L is below and background for the questionnaire is available at http://www.euroqol.org/home.html.

Patients will complete the IEC/IRB approved version of the assessment on an electronic device or other format (ie, paper form), as appropriate.

Euro-QoL5D-5L (EQ-5D-5L) – English Version for the US

[figure not shown]
Under each heading, please check the ONE box that best describes your health TODAY.

Mobility	
I have no problems walking	
I have slight problems walking	
I have moderate problems walking	
I have severe problems walking	
I am unable to walk	
Self-Care	
I have no problems washing or dressing myself	
I have slight problems washing or dressing myself	
I have moderate problems washing or dressing myself	
I have severe problems washing or dressing myself	
I am unable to wash or dress myself	
Usual Activities (e.g. work, study, housework, family or leisure activities)	
I have no problems with doing my usual activities	
I have slight problems with doing my usual activities	
I have moderate problems with doing my usual activities	
I have severe problems with doing my usual activities	
I am unable to do my usual activities	

Rucaparib	pharma&
Clinical Study Protocol: CO-338-087 Amendment 5	16 June 2023
Pain/Discomfort	
I have no pain or discomfort	
I have slight pain or discomfort	
I have moderate pain or discomfort	
I have severe pain or discomfort	
I have extreme pain or discomfort	
Anxiety/Depression	
I am not anxious or depressed	
I am slightly anxious or depressed	
I am moderately anxious or depressed	
I am severely anxious or depressed	
I am extremely anxious or depressed	

- We would like to know how good or bad your health is TODAY.
- This scale is numbered from 0 to 100.
- 100 means the best health you can imagine.
 0 means the worst health you can imagine.
- . Mark an X on the scale to indicate how your health is TODAY.
- Now, please write the number you marked on the scale in the box below.

YOUR HEALTH TODAY =

Appendix 7 Management Algorithms for Immuno-Oncology Agents

These general guidelines (28 September 2020; CTCAE v5.0) constitute guidance to the Investigator and may be supplemented by discussions with the Medical Monitor representing the Sponsor. The guidance applies to all immuno-oncology agents and regimens.

A general principle is that differential diagnosis should be diligently evaluated according to standard medical practice. Non-inflammatory etiologies should be considered and appropriately treated.

[figure not shown]
Corticosteroids are a primary therapy for immuno-oncology drug-related adverse events. The oral equivalent of the recommended IV doses may be considered for ambulatory patients with low-grade toxicity. The lower bioavailability of oral corticosteroids should be taken into account when switching to the equivalent dose of oral corticosteroids.

Consultation with a medical or surgical specialist, especially prior to an invasive diagnostic or therapeutic procedure, is recommended.

The frequency and severity of the related adverse events covered by these algorithms will depend on the immuno-oncology agent or regimen being used.

GI Adverse Event Management Algorithm

Rule out non-inflammatory causes. If non-inflammatory cause is identified, treat accordingly and continue I-O therapy. Opiates/narcotics may mask symptoms of perforation. Infliximab should not be used in cases of perforation or sepsis.

[figure not shown]

Patients on IV steroids may be switched to an equivalent dose of oral corticosteroids (eg, prednisone) at start of tapering or earlier, after sustained clinical improvement is observed. Lower bioavailability of oral corticosteroids should be taken into account when switching to the equivalent dose of oral corticosteroids.

*Discontinue for Grade 4 diarrhea or colitis. For Grade 3 diarrhea or colitis, I-O therapy can be delayed. I-O therapy can be resumed when symptoms improve to Grade 1. Please refer to the protocol for dose delay and discontinue criteria for other combinations.

Renal Adverse Event Management Algorithm – Rucaparib^a and Nivolumab

Rule out non-inflammatory causes. If non-inflammatory cause, treat accordingly and continue I-O therapy.

[figure not shown]

Patients on IV steroids may be switched to an equivalent dose of oral corticosteroids (eg, prednisone) at start of tapering or earlier, after sustained clinical improvement is observed. Lower bioavailability of oral corticosteroids should be taken into account when switching to the equivalent dose of oral corticosteroids.

^a Baseline for creatinine will be considered pre-dose to the first IV infusion.

Pulmonary Adverse Event Management Algorithm

Rule out non-inflammatory causes. If non-inflammatory cause, treat accordingly and continue I-O therapy. Evaluate with imaging and pulmonary consultation.

[figure not shown]

Patients on IV steroids may be switched to an equivalent dose of oral corticosteroids (eg, prednisone) at start of tapering or earlier, after sustained clinical improvement is observed. Lower bioavailability of oral corticosteroids should be taken into account when switching to the equivalent dose of oral corticosteroids.

Hepatic Adverse Event Management Algorithm-Rucaparib^a and Nivolumab

Rule out non-inflammatory causes. If non-inflammatory cause, treat accordingly and continue I-O therapy.

Consider imaging for obstruction.

Patients on IV steroids may be switched to an equivalent dose of oral corticosteroids (eg, prednisone) at start of tapering or earlier, after sustained clinical improvement is observed. Lower bioavailability of oral corticosteroids should be taken into account when switching to the equivalent dose of oral corticosteroids.

[^] Please refer to the protocol dose delay and discontinue criteria for specific details.

[figure not shown]
^{*} The recommended starting dose for AST or ALT > 20 \times ULN or bilirubin > 10 \times ULN is 2 mg/kg/day methylprednisolone IV.

^a Rucaparib may cause transient AST and/or ALT elevations (without increased total bilirubin) in Cycle 1. Please see Section 5.6.1.2 and Section 5.6.4.2 for details about when a hold or discontinuation of IV drug is not required due to a background of AST and/or ALT elevations that are due to oral drug.

Endocrinopathy Adverse Event Management Algorithm

Rule out non-inflammatory causes. If non-inflammatory cause, treat accordingly and continue I-O therapy.

[figure not shown]
Consider visual field testing, endocrinology consultation, and imaging.

Patients on IV steroids may be switched to an equivalent dose of oral corticosteroids (eg, prednisone) at start of tapering or earlier, after sustained clinical improvement is observed. Lower bioavailability of oral corticosteroids should be taken into account when switching to the equivalent dose of oral corticosteroids.

Skin Adverse Event Management Algorithm

Rule out non-inflammatory causes. If non-inflammatory cause, treat accordingly and continue I-O therapy.

Patients on IV steroids may be switched to an equivalent dose of oral corticosteroids (eg, prednisone) at start of tapering or earlier, after sustained clinical improvement is observed. Lower bioavailability of oral corticosteroids should be taken into account when switching to the equivalent dose of oral corticosteroids.

[figure not shown]
^{*} Refer to NCI CTCAE v5 for term-specific grading criteria.

[^] If Steven-Johnson Syndrome (SIS), toxic epidermal necrosis (TEN), Drug Reaction with Eosinophilia and Systemic Symptoms (DRESS) is suspected, withhold I-O therapy and refer patient for specialized care for assessment and treatment. If SIS, TEN, or DRESS is diagnosed, permanently discontinue I-O therapy.

16 June 2023

Neurological Adverse Event Management Algorithm

Rule out non-inflammatory causes. If non-inflammatory cause, treat accordingly and continue I-O therapy.

[figure not shown]

Patients on IV steroids may be switched to an equivalent dose of oral corticosteroids (eg, prednisone) at start of tapering or earlier, after sustained clinical improvement is observed. Lower bioavailability of oral corticosteroids should be taken into account when switching to the equivalent dose of oral corticosteroids.

[^] Discontinue for any grade myasthenia gravis, Guillain-Barre syndrome, treatment-related myelitis, or encephalitis.

Myocarditis Adverse Event Management Algorithm

Rule out non-inflammatory causes. If non-inflammatory cause, treat accordingly and continue I-O therapy.

Patients on IV steroids may be switched to an equivalent dose of oral corticosteroids (eg, prednisone) at start of tapering or earlier, after sustained clinical improvement is observed. Lower bioavailability of oral corticosteroids should be taken into account when switching to the equivalent dose of oral corticosteroids.

Prophylactic antibiotics should be considered in the setting on ongoing immunosuppression.

Clinical Study Protocol: CO-338-087 Amendment 5

Appendix 8 Adverse Event Criteria for Delay, Resume, and Discontinue of Nivolumab

Drug-Related Adverse Event (AE) per CTCAE V5	Severity	Action Taken	Clarifications, Exceptions, and Resume Criteria
Gastrointestinal			
Colitis or Diarrhea	Grade 2	Delay dose	Dosing may resume when AE resolves to baseline
	Grade 3	Nivolumab monotherapy: Delay dose	Dosing may resume when AE resolves to baseline
	Grade 4	Permanently discontinue	
Renal			
Serum Creatinine Increased	Grade 2 or 3	Delay dose	Dosing may resume when AE resolves to Grade ≤ 1 or baseline value
	Grade 4	Permanently discontinue	
Pulmonary			
Pneumonitis	Grade 2	Delay dose	Dosing may resume after pneumonitis has resolved to \leq Grade 1.
	Grade 3 or 4	Permanently discontinue	
Hepatic			
Aspartate aminotransferase (AST), alanine aminotransferase (ALT), or total bilirubin (T.bili) increased	AST or ALT > 3x and ≤5x upper limit of normal (ULN) or T.Bili >1.5x and ≤3x ULN, regardless of baseline value	Delay dose	Dosing may resume when laboratory values return to baseline.
	AST or ALT > 5 x ULN or T. bili > 3 x ULN, regardless of baseline value	Permanently discontinue	
	Concurrent AST or ALT > 3 x ULN and T.bili > 2 x ULN, regardless of baseline value	Permanently discontinue	

Endocrinopathy			
Adrenal Insufficiency	Grade 2 adrenal insufficiency	Delay dose	Dosing may resume after adequately controlled with hormone replacement.
	Grade 3 or 4 adrenal insufficiency or adrenal crisis	Delay dose or permanently discontinue	Mandatory discussion with and approval from the Medical Monitor needed prior to resuming therapy. If adrenal insufficiency resolves or is adequately controlled with physiologic hormone replacement, participant may not require discontinuation of study drug.
Hyperglycemia	Hyperglycemia requiring initiation or change in daily management (Grade 2 or 3)	Delay dose	Dosing may resume if hyperglycemia resolves to Grade ≤1 or baseline value, or is adequately controlled with glucose-controlling agents.
	Grade 4	Delay dose or permanently discontinue	Mandatory discussion with and approval from the Medical Monitor needed prior to resuming therapy. If hyperglycemia resolves, or is adequately controlled with glucose-controlling agents, participant may not require discontinuation of study drug.
Hypophysitis/Hypopituitarism	Symptomatic Grade 1-3 that is also associated with corresponding abnormal lab and/or pituitary scan	Delay dose	Dosing may resume if endocrinopathy resolves to be asymptomatic, or is adequately controlled with only physiologic hormone replacement.
	Grade 4	Delay dose or permanently discontinue	Mandatory discussion with and approval from the Medical Monitor needed prior to resuming therapy. If endocrinopathy resolves or is adequately controlled with physiologic hormone replacement, participant may not require discontinuation of study drug.
Hyperthyroidism or Hypothyroidism	Grade 2 or 3	Delay dose	Dosing may resume if endocrinopathy resolves to be asymptomatic, or is adequately controlled with only physiologic hormone replacement or other medical management.
	Grade 4	Delay dose or permanently discontinue	Mandatory discussion with and approval from the Medical Monitor needed prior to resuming therapy. If endocrinopathy resolves or is adequately controlled with physiologic hormone replacement or other medical management, participant may not require discontinuation of study drug.

Skin			
Rash	Grade 2 rash covering >30% body surface area or Grade 3 rash	Delay dose	Dosing may resume when rash reduces to ≤10% body surface area
	Suspected Stevens-Johnson syndrome (SJS), toxic epidermal necrolysis (TEN) or drug reaction with eosinophilia and systemic symptoms (DRESS)	Delay dose	Dosing may resume if SJS, TEN, or DRESS is ruled out and rash reduces to is ≤10% body surface area
	Grade 4 rash or confirmed SJS,TEN, or DRESS	Permanently discontinue	
Neurological			
Guillain-Barre Syndrome (GBS)	Any Grade	Permanently discontinue	
Myasthenia Gravis (MG)	Any Grade	Permanently discontinue	
Encephalitis	Any Grade encephalitis	Delay dose	After workup for differential diagnosis, (i.e. infection, tumor-related), if encephalitis is not drug related, then dosing may resume when AE resolves
	Any Grade drug-related encephalitis	Permanently discontinue	
Myelitis	Any Grade myelitis	Delay dose	After workup for differential diagnosis, (i.e. infection, tumor-related), if myelitis is not drug related, then dosing may resume when AE resolves
	Any Grade drug-related myelitis	Permanently discontinue	
Neurological (other than GBS, MG, encephalitis, or myelitis)	Grade 2	Delay dose	Dosing may resume when AE resolves to baseline
	Grade 3 or 4	Permanently discontinue	
Myocarditis			
Myocarditis	Symptoms induced from mild to moderate activity or exertion	Delay dose	Dosing may resume after myocarditis has resolved

	Severe or life threatening, with symptoms at rest or with minimal activity or exertion, and/or where intervention indicated.	Permanently discontinue	
Other Clinical AE			
Pancreatitis: Amylase or Lipase increased	Grade 3 with symptoms	Delay dose	Note: Grade 3 increased amylase or lipase without signs or symptoms of pancreatitis does not require dose delay. Dosing may resume when patient becomes asymptomatic.
	Grade 4	Permanently discontinue	
Uveitis	Grade 2 uveitis	Delay dose	Dosing may resume if uveitis responds to topical therapy (eye drops) and after uveitis resolves to Grade ≤ 1 or baseline. If patient requires oral steroids for uveitis, then permanently discontinue study drug.
	Grade 3 or 4 uveitis	Permanently discontinue	
Other Drug-Related AE (not listed above)	Grade 2 non-skin AE, except fatigue	Delay dose	Dosing may resume when AE resolves to Grade ≤ 1 or baseline value.
	Grade 3 AE - First occurrence lasting ≤ 7 days	Delay dose	Dosing may resume when AE resolves to Grade ≤ 1 or baseline value.
	Grade 3 AE- First occurrence lasting > 7 days	Permanently discontinue	
	Recurrence of Grade 3 AE of any duration	Permanently discontinue	
	Grade 4 or Life-threatening adverse reaction	Permanently discontinue	
Other Lab abnormalities			
Other Drug-Related lab abnormality (not listed above)	Grade 3	Delay dose	Exceptions: No delay required for: Grade 3 lymphopenia Permanent Discontinuation for: Grade 3
			thrombocytopenia > 7 days or associated with bleeding.

Rucaparib
Clinical Study Protocol: CO-338-087 Amendment 5
16 June 2023

	Grade 4	Permanently discontinue	 Exceptions: The following events do not require discontinuation of study drug: Grade 4 neutropenia ≤ 7 days Grade 4 lymphopenia or leukopenia Grade 4 isolated electrolyte imbalances/abnormalities that are not associated with clinical sequelae and are responding to supplementation/appropriate management within
			72 hours of their onset
Infusion Reactions (manifested by fever, chills, rigors, headache, rash, pruritus, arthralgia, hypotension, hypertension, bronchospasm, or other allergic-like reactions.)			
Hypersensitivity reaction or infusion reaction	Grade 3 or 4	Permanently discontinue	Refer to Section 7.4.4 on Treatment of Related Infusion Reactions

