5.6.1.2 Nivolumab/IV Placebo

IV study drug administration should be held for the following:

- Grade 2 non-skin, drug-related AE, with the exception of fatigue and pancreatitis
- Grade 2 drug-related creatinine (≥ 1.5-3.0 × baseline; > 1.5-3.0 × ULN) or Grade 3 drug-related creatinine (> 3.0 × baseline; > 3.0-6.0 × ULN) abnormalities
 - Baseline is defined as the creatinine value obtained prior to dosing the IV drug on C2D1, or first dose of IV drug, whichever is later

Note: Elevated creatinine is frequently observed with rucaparib monotherapy. Rucaparib is a potent inhibitor of MATE1 and MATE2-K transporters, which are involved in active secretion of creatinine. Rucaparib-mediated creatinine elevation occurs early in treatment (Day 15 of Cycle 1), and is not typically accompanied by elevations in urea (blood urea nitrogen [BUN]). Creatinine elevation resolves with dose holds of rucaparib and recurs with rechallenge. Rucaparib associated creatinine elevation has not been associated with evidence or reports of permanent renal impairment.

- Drug-related AST, ALT, and/or bilirubin abnormalities with the range of AST or ALT > $3 \times \text{and} \le 5 \times \text{ULN}$ or total bilirubin > $1.5 \times \text{and} \le 3 \times \text{ULN}$, regardless of baseline value
 - For participants with the above range of AST or ALT elevations with onset during dosing of the first cycle of oral study drug, IV study treatment hold is not required if AST/ALT elevations begin to resolve before the next scheduled infusion and toxicity is considered to be mainly related to oral study treatment. If the patient has an existing such elevation, and a subsequent AST/ALT increase of more than 20% is observed following infusion of IV study drug, the next IV study drug administration will be held and, if further increase is observed, the Hepatic Adverse Event Management Algorithm will be followed (see Appendix 7). If AST or ALT or total bilirubin elevations are considered mainly related to IV drug, IV drug dosing may resume when laboratory values return to baseline. IV drug should be discontinued at concurrent AST or ALT > 3 × ULN and total bilirubin > 2 × ULN, regardless of baseline value.
 - For participants with ALT or AST elevations > 3 × ULN or total bilirubin > 1.5 × ULN regardless of baseline value that begin after Cycle 3, the Hepatic Adverse Event Management Algorithm will be followed (see Appendix 7).

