Note: Rucaparib may cause transient AST and/or ALT elevations (without increased total bilirubin) at Cycle 1, Day 15 that begin to resolve by Day 29, even with continued rucaparib dosing.

Grade 2 or 3 colitis or diarrhea

- Grade 3 pancreatitis with symptoms. Grade 3 increased amylase or lipase without signs or symptoms of pancreatitis does not require dose delay
- Grade 2 rash covering > 30% body surface area or Grade 3 drug-related skin AE. Suspected Stevens-Johnson Syndrome (SJS), toxic epidermal necrolysis (TEN), or drug reaction with eosinophilia and systemic symptoms (DRESS)
- Endocrinopathies met the following criteria:
 - Grade 2 adrenal insufficiency.
 - Grade 2 or 3 hyperglycemia requiring initiation or change in daily management.
 - Grade 1-3 hypophysitis/hypopituitarism that is symptomatic and also associated with corresponding abnormal lab and/or pituitary scan.
 - Grade 2 or 3 hyperthyroidism or hypothyroidism.
- Grade 2 uveitis.
- Grade 2 neurological (other than Guillain-Barre Syndrome [GBS], myasthenia gravis [MG], encephalitis, or myelitis).
- Any grade of encephalitis or myelitis. After workup for differential diagnosis, (ie, infection, tumor-related), if it is not drug related, then dosing may resume when AE resolves.
- Myocarditis with symptoms induced from mild to moderate activity or exertion.
- Other Grade 3 drug-related AE with first occurrence lasting ≤ 7 days.
- Grade 3 drug-related laboratory abnormality (not listed above), with the following exceptions:
 - Grade 3 lymphopenia or Grade 3 increased amylase or lipase without signs or symptoms of pancreatitis does not require dose delay.
 - Grade 3 thrombocytopenia > 7 days or associated with bleeding requires for dose discontinuation.
 - AST, ALT, and/or total bilirubin elevations with a range of AST or ALT > 5 × ULN or total bilirubin > 3 × ULN, regardless of baseline value, will require dose delay or discontinuation. (See Section 5.6.4.2)*
- Any AE, laboratory abnormality, or intercurrent illness that, in the judgment of the investigator, warrants delaying the dose of study medication.

Participants who require dose hold should be re-evaluated weekly or more frequently if clinically indicated and resume dosing during the next scheduled dosing window (Cycle X, Day 1 ± 3 days) after re-treatment criteria are met (Section 5.6.2).

Please refer to Appendix 8: AE Criteria for Delay, Resume and Discontinue of Nivolumab.

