5.6.2.2 Nivolumab/IV Placebo

Participants may resume treatment with IV study drug when the drug-related AE(s) improve to Grade ≤ 1 or resolve to baseline value, with the following exceptions:

- Participants may resume treatment in the presence of Grade 2 fatigue and pancreatitis.
- Participants who are suspected with SJS, TEN, or DRESS may resume treatment if SJS, TEN, or DRESS are ruled out and rash reduces to < 10% body surface area.
- For participants with elevated AST, ALT, or total bilirubin elevations, dosing may resume when laboratory values return to baseline and management with corticosteroids, if needed, is complete.
- Drug-related pulmonary toxicity, diarrhea or colitis must have resolved to baseline before treatment is resumed. Participants with persistent Grade 1 pneumonitis after completion of a steroid taper over at least 1 month may be eligible for retreatment if discussed with and approved by the study medical monitor.
- Participants with Grade 2 uveitis may resume treatment if uveitis responds to topical therapy (eye drops) and after uveitis resolves to Grade ≤ 1 or baseline. If patient requires oral steroids for uveitis, then permanently discontinue study drug.
- For visual complaints, patients should be referred to an ophthalmologist following the guidance in Section 7.1.10 of the nivolumab Investigator's Brochure.

Participants with drug-related endocrinopathies adequately controlled with only physiologic hormone replacement may resume treatment after consultation with the study medical monitor.

Participants with Grade 2 neurological (other than GBS, MG, encephalitis, or myelitis) may resume when AE resolves to baseline

If the criteria to resume treatment are met, the patient should restart treatment at the next scheduled timepoint per protocol. However, if the treatment is withheld past the window period of the next scheduled timepoint per protocol to ensure adequate recovery from the adverse event or tapering of immunosuppression, the dosing should continue to be withheld until the subsequent scheduled timepoint.

If treatment is withheld > 8 weeks from the last dose (2 or more consecutive IV drug cycles missed), the subject must be permanently discontinued from study therapy, except as specified in Section 5.6.4.2.

Please refer to Appendix 8: AE Criteria for Delay, Resume and Discontinue of Nivolumab.

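### Appendix 8 lets IV drug restart after Grade 2 pneumonitis at Grade 1 or less, which contradicts the stricter restart rule in Protocol Section 5.6.2.2

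*Protocol*

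**What the plan says.** All of this is current Amendment 5 text.

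- **Hold.** Protocol 5.6.1.2 holds IV drug for a "Grade 2 non-skin, drug-related AE, with the exception of fatigue and pancreatitis". Pneumonitis is not excepted, so a Grade 2 drug-related event is held. The Appendix 8 pneumonitis row also delays the dose at Grade 2.
- **Which section governs restart.** 5.6.1.2 says that held patients "resume dosing during the next scheduled dosing window (Cycle X, Day 1 ± 3 days) after re-treatment criteria are met", and the sentence then cites Section 5.6.2 in parentheses.
- **Restart, body text.** 5.6.2.2 allows IV drug again "when the drug-related AE(s) improve to Grade ≤ 1 or resolve to baseline value, with the following exceptions". One exception reads "Drug-related pulmonary toxicity, diarrhea or colitis must have resolved to baseline before treatment is resumed". The only relaxation is that participants with "persistent Grade 1 pneumonitis after completion of a steroid taper over at least 1 month may be eligible for retreatment", provided that the medical monitor has discussed and approved it.
- **Restart, table.** For Grade 2 pneumonitis, Appendix 8 says "Dosing may resume after pneumonitis has resolved to" Grade 1 or less. The cell mentions neither baseline, nor a taper, nor the monitor.
- **Cross-references.** Sections 5.6, 5.6.1.2, 5.6.2.2 and 5.6.4.2 all send the reader to Appendix 8. None says what to do if the table and the body disagree.

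**The concern.** Section 5.6.2.2 takes pulmonary toxicity out of the general Grade 1 rule; the Appendix 8 row puts pneumonitis back under it. Appendix 8 is laid out as a lookup table of when to delay, resume and stop nivolumab, so it is a natural page to open when deciding on an infusion. An investigator using it could give IV drug to a patient who still has Grade 1 pneumonitis, without a completed taper and without the medical monitor knowing.

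The protocol treats this event as serious: the sponsor designates pneumonitis an adverse event of special interest (Section 1.1.1.2.3.1), and Grade 3 or 4 pneumonitis ends IV dosing (Appendix 8; Grade 3 also in 5.6.4.2). What is at stake is a dosing safeguard, not a trial result.

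**Working it through.** There is no figure to reproduce. The check is to set the two rules side by side for a patient held for Grade 2 drug-related pneumonitis.

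| State when the next IV dose is considered | 5.6.2.2 | Appendix 8 |
|---|---|---|
| Grade 2 | Hold | Hold |
| Grade 1, taper of at least 1 month not completed | Hold | May resume |
| Grade 1, taper completed, no monitor approval | Hold | May resume |
| Grade 1, taper completed, monitor approves | May resume | May resume |
| Back to baseline, no pneumonitis | May resume | May resume |

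The rules differ in the second and third rows only.

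**Is baseline stricter than Grade 1?** Normally yes. Exclusion criterion 5 (Section 4.3) bars active pneumonitis at entry, and Section 9.1 defines baseline as the last measurement on or before the first day of study drug. Baseline therefore normally means no pneumonitis. This is an inference, because 5.6.2.2 does not define baseline for pulmonary events.

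**Could the cell just be shorthand?** Two features of Appendix 8 speak against it.

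1. The sentence in 5.6.2.2 that covers pulmonary toxicity also covers diarrhea and colitis. For those, Appendix 8 does carry the stricter endpoint: "Dosing may resume when AE resolves to baseline". Of the events in that sentence, only the pneumonitis row departs from it.
2. The table holds such conditions elsewhere. It requires medical monitor approval before resuming after Grade 3 or 4 adrenal insufficiency and after Grade 4 hyperglycemia, hypophysitis or thyroid events, and it sets a steroid condition for uveitis.

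**Were patients still being dosed at Amendment 5?** Section 9.2.2 expected randomization to close in the third quarter of 2020. Take the latest planned dates:

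- last randomization 30 September 2020, plus 3 days to first oral dose = 3 October 2020;
- plus 28 days to Cycle 2 Day 1 = 31 October 2020;
- plus the 24-month cap = 31 October 2022;
- to Amendment 5 on 16 June 2023: 30 + 31 + 31 + 28 + 31 + 30 + 31 + 16 = 228 days, about 7.5 months.

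This assumes that enrollment closed as planned and that Cycle 2 was not delayed. Section 7.1 of the combination-comparison SAP also expects every patient to be off treatment by its visit cut-off.

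**The case against.** The strongest reply is that the protocol already settles the matter. Section 5.6.1.2 names Section 5.6.2 as the restart criteria, and 5.6.2.2 says that pulmonary toxicity must resolve, whereas Appendix 8 says only that dosing may resume. Following 5.6.2.2 satisfies both texts. This stands. A reader might infer that the protocol permits infusion at unresolved Grade 1, so that an investigator could do it and remain compliant. The documents do not support that: such an infusion would breach 5.6.2.2. What remains is a misleading table.

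A second reply is that Appendix 8 is an abridged companion to Sections 5.6.1 to 5.6.4, where Section 5.6 says the detail lies. Other rows drop body conditions too. The Grade 2 or 3 thyroid row omits the monitor consultation that 5.6.2.2 asks for, and the row for AST or ALT above 5 × ULN omits the exceptions in 5.6.4.2. This stands in part. Abridgement could explain the missing taper and approval. It does not explain a different endpoint, Grade 1 or less in place of baseline.

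Third, Figure 2 and the Appendix 7 pulmonary algorithm are not visible in the text available and may add conditions. That is a fair limit, but neither could remove the conflict between two texts that are visible.

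Two further inferences go too far. One is that the stricter rule costs a patient at least one 28-day cycle. That depends on when the taper starts and on how a month is counted, and the documents fix neither. The other is that Section 5.7.2, on oral re-treatment after pneumonitis, conflicts with the rule for stopping both drugs. It does not: 5.6.4 applies as a general rule whether or not 5.7.2 cites it, and 5.7.2 already requires consulting the medical monitor.

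**Conclusion.** The inconsistency is real and worth correcting, as a minor safety-text point. Appendix 8 states a looser IV restart rule for Grade 2 pneumonitis than the section that governs restart. The two rules part only for patients who are still at Grade 1 and have not both completed the taper and obtained monitor approval.

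The size cannot be given. The documents state no pneumonitis incidence, and on planned dates few or no patients may still have been on treatment when Amendment 5 was issued, so the correction may do no more than put the text right. No efficacy analysis, alpha, power or sample size is affected.

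The conclusion rests on reading baseline as no pneumonitis, which exclusion criterion 5 makes the normal case.

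**What to change.** Change one cell: Appendix 8, Pulmonary, Pneumonitis, Grade 2, resume criteria. Keep the opening words, "Dosing may resume after pneumonitis has resolved to", and end the sentence with *baseline* instead of Grade 1 or less. Then add: *Persistent Grade 1: only once a steroid taper lasting at least 1 month is complete and the medical monitor has approved (Section 5.6.2.2).*

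This restates the sponsor's own rule and adds no new restriction. The cost is that an occasional patient whose site would have used the table restarts IV drug later, or not at all. One reason is that, if recovery or the taper runs past the dosing window, 5.6.2.2 already says that "the dosing should continue to be withheld until the subsequent scheduled timepoint". A delay of more than 8 weeks for a prolonged steroid taper is already allowed under 5.6.4.2, so the change need not force discontinuation.
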